1.1 Background

Medicines' management, especially monitoring therapeutic and adverse effects for older adults, is an area of growing importance (Care Quality Commission, 2019; NHS Scotland, 2018; NICE, 2015; Oscanoa et al., 2017; WHO, 2017, 2019).

Medicines prescribed for the older population can lead to medicine-related frailty (Saum et al., 2017) and adverse drug reactions due to polypharmacy and altered pharmacokinetics (Chetty et al., 2018). Adverse drug reactions cause around 5-8% of unplanned hospital admissions in the UK, costing the NHS £1.5-2.5bn pa (NICE, 2015), apart from the avoidable patient harm.

GP's are increasingly prescribing more medications that would have been prescribed by specialists in the past (Wood, 2020). GMC published in its report Investigating the prevalence and causes of prescribing errors in general practice that 1 in 20 prescriptions contained an error in terms of medication or monitoring, affecting 1 in 8 patients (2012). It is well known that the number of people with multiple conditions is increasing, with older people more likely to live with a long-term disease (Health Foundation, 2018). The problems persist, and polypharmacy presents a major threat to patient safety internationally (WHO, 2019).

Many adverse drug reactions could be prevented with improved monitoring (Gabe et al., 2011). Doctors, pharmacists and nurses are regularly involved with aspects of medicine management, yet there is often a lack of clarity in who should monitor for the side effects and both doctors and nurses think that the other profession monitors patients for adverse effects of prescribed medicines (Logan et al 2020). ADRe Profile (Jordan et al 2014; Jordan et al 2015) represents an innovative nurse-led tool, which collates patient observation and self-reported data to identify a potential link of any problems with the medicines prescribed.

1.2 Preclinical Data

The study population are older people who are prescribed 5 or more medications daily. Implied is the presence of one or more long-term conditions, particularly cardiovascular, respiratory, endocrine, neurological, mental health and musculoskeletal conditions. Implementation of guidelines for management of these conditions results in prescriptions. An increase in the number of long-term conditions increases the complexity of therapeutic and pharmacological management and is associated with the use of multiple medications. Globally, the numbers of older people are growing and more live with multimorbidity (WHO, 2016). The UK incidence of long-term health problems in people older than 65 years was 8.75 million in 2019 (Office for National Statistics [ONS], 2020). This translates to over 2 in 3 people over 65 having a long-term condition. In England, simulation projections estimate that between 2015 and 2035, the number of older people with more than 4

SU Non CTIMP Healthcare Research Protocol

diseases will double and a third of these will have mental health problems (Kingston et al., 2018). Polypharmacy is hence a phenomenon that likely to increase (Duerden et al., 2013) and medication safety has been identified as the theme of the WHO third global safety challenge (WHO, 2017).

1.3 Clinical Data

Medication monitoring and monitoring patients for potential adverse drug reactions has been described as an 'orphan task' in the past due to its position on the interprofessional boundary between pharmacy, medicine and nursing and the subsequent deficiency in ownership (Jordan, 2002, Jordan et al., 2016). Recent studies confirm the lack of clarity of the nurses' roles in medication management (De Baetselier et al., 2019) and effective teamwork has been affirmed as a facilitator of safe management of polypharmacy (WHO, 2019), and medication management overall (WHO, 2017). ADRe Profile is an instrument that involves nurses, pharmacists, prescribers and patients in monitoring for adverse drug reactions to medicines. Nurses and patients identify the problems and may solve some of them, pharmacists review the medicines and prescribers may be provided with recommendations to consider adjustment of the prescriptions.

To date, two randomised controlled trials and five observational/before and after studies have investigated the clinical impact of the ADRe Profile. In total, 168 study participants had the ADRe Profile implemented. Majority of the participants were prescribed mental health medicines (antipsychotics, antidepressants or anti-epileptics), one study included patients with respiratory diseases, taking bronchodilators, corticosteroids or leukotriene receptor antagonists. The setting was mostly in the community, with 3 nursing homes, 3 community mental health settings and one outpatient respiratory clinic.

In two of the community mental health settings, the mean number of problems actioned increased from 0.35 with no ADRe Profile to 3 with ADRe Profile (Jordan et al., 2002; Jordan, 2002). Little change in the number of problems actioned was noted in the comparator groups. The mean number of problems detected increased from 2 without the Profile to 9 with the Profile in one of the studies (Jordan, 2002), no information was offered in the other study. Most actions taken were to alleviate physical health problems.

Another study from an acute mental health service setting identified and addressed health problems for all participants (the mean increase of actions taken was 11.9, SD = 4.7, range 2-20) (Jones et al., 2016). Some of the problems identified were orthostatic hypotension, hypertension, constipation or inadequate diet, two of the

SU Non CTIMP Healthcare Research Protocol
problems were potentially life-threatening (cardiac arrhythmia with chest pain and breathlessness and valproate-induced pancreatitis).

The findings of the three studies from care homes are consistent with the above. 11 participants in a private sector nursing home had at least one problem ameliorated (mean = 4.9, SD = 3.6, range = 1-11), for example previously un-noticed abnormal movements, postural hypotension and pain (Jordan et al., 2014). Majority of residents in the other two care home studies had at least one problem ameliorated. The use of the Profile prompted documentation and treatment of pain, balance, cognitive decline, irritability and other problems (Jordan et al., 2015) and resulted in effective analgesia (7 out of 8 residents with reported pain), amelioration of sedation, confusion or hallucinations (on discontinuation of antipsychotics), changes to care to prevent further falls (5 out of 9 residents with identified falls) (Jordan et al., 2019). Jordan and colleagues (2015) also report a reduction in mental health prescriptions associated with the use of the Profile (aOR 4.45, 1.15-17.22), even though total number of medicines prescribed has not changed, partly due to increase in analgesia.

A trial in a nurse-led respiratory outpatient clinic (Gabe et al., 2014) reported more problems identified and actions taken to ameliorate the problems for the ADRe Profile intervention arm. Examples of problems identified was muscular weakness and pain, dry mouth/dental/oral problems, tendency to bruising and others.

In all studies, the use of ADRe Profile resulted in identification of previously unattended problems and empowerment of the nurse to initiate actions to address the problems. No harm from completing the checklist has been recorded. The ADRe Profile positively contributed to the quality and safety of care.

1.4 Rationale and Risks/Benefits

This study concerns optimisation of medicines monitoring and multidisciplinary team involvement in medicines management and optimisation. Similar projects have not encountered major ethical, legal or management issues, and we do not envisage any here. The Adverse Drug Reaction (ADRe) Profiles for nurse-led medicines monitoring have benefitted patients in all previous trials and observation studies and no harms have been reported. In this study, the instrument will be adapted for use in general practices and the feasibility of its adoption will be explored by the researchers. The ADRe Profile has recently been endorsed by the Royal Pharmaceutical Society and All Wales Medicines Strategy Group (AWMSG). Embedding the ADRe Profiles thus represents an addition of an established

SU Non CTIMP Healthcare Research Protocol

instrument to the nursing documentation and the risk of physical and emotional harm from the instrument is predicted to be minimal, and no more than in routine clinical interviews. Vital signs will be recorded. Results of ECGs, lung function tests and laboratory results will be noted as 'present / absent': these tests are not part of the study.

Risks and burdens according to study participants:

Content validity index and construct validity respondents: we foresee no potential risk of physical or emotional harm to competent adult respondents completing an electronic document from their own computers in their own time.

Cognitive interview participants: we foresee no potential risk of physical or emotional harm to competent adult respondents reading through a draft instrument with a trained research fellow in their own time. Respondents will be asked questions on validity and interpretation of the instrument. They will not be asked any questions about themselves or expected to divulge any personal information. No identifiable data will be collected.

Service users – ADRe Profile completion: Previous work in the nursing homes and a respiratory clinic indicates that no physical or emotional harms emanate from this intervention, and the physical health of all participants has benefitted (Gabe et al., 2014; Jordan et al., 2015; Jones et al., 2016; Jordan et al., 2019). We do not foresee any risks of physical or emotional harm in this or future studies. We foresee no legal or organisational risk from this study. Any changes to patient management will be based on the professional judgment of staff delivering routine care, and not directed by the study procedures. The intervention only aims to enhance patient monitoring to inform professional judgement. All questions and observations are of a nature that should be pursued under routine care. Time will be required by nurses to complete the ADRe profiles; however, the clinical gains reported in care home studies are likely to outweigh any diversion of resources (Jordan et al., 2015, 2014, 2019). Should any answers in the ADRe Profile raise the nurse-researcher's concern about physical or mental health and well-being of the participant, clinical judgment will be applied and the participant will be advised or referred to their general practitioner. Completed ADRe profiles will be passed to the pharmacist associated with the GP practice and academic pharmacists and thence prescribers.

Balance of risks and benefits of participation in the ADRe Profile completion:

Risk	Benefit

- Breach of confidentiality- Adjustment of medicines, additional prescriptions or de-prescribing- Possible additional health service contacts- Possible misunderstanding (esp. people who have difficulty speaking or understanding English)	
- Additional medication review- Potential identification and amelioration of health and well-being problems- Opportunity to discuss therapeutic regimen with academic clinicians, and access ADRe's supporting information.

Survey and semi-structured interviews: stakeholder perspectives will be sought from service users, nurses, pharmacists and GP's. There are no significant risks attached to these interviews, however; should any participant become upset/distressed during the interviews, the researcher, who is experienced at de-escalating difficult/emotional situations, will deal with the situation. Potential risks and burdens will be described in the participant information sheet in such a way that participants can clearly understand what will be involved if they consent to take part. The principles of GCP training and the standard operating procedures of the Swansea Clinical Trials Unit will be followed throughout. The trials unit has granted access to their standard operating procedures.

Covid 19 pandemic: The researchers will ensure compliance with health and safety requirements in the context of the pandemic, and measures that adhere to current infection control guidelines (e.g. protective equipment, social distancing). Alternative arrangements have been planned to protect the potentially vulnerable participants from the effects of Covid 19. If by the time the trial is taking place it would be deemed that in-person exposure would increase the participants' risk of contracting Covid 19, all contact will be only electronic, through video calls, phone calls or by post. We will be guided by Welsh government responses to the pandemic.

2. Trial Objectives and Design

2.1 Trial Objectives

Primary Objectives

- To establish the suitability/effectiveness of ADRe Profile for video call completion
- To establish whether patients could complete parts of ADRe Profile themselves
- To explore whether the ADRe Profile identifies health problems that could be attributable to polypharmacy and ameliorated (and record any changes to care, benefits or harms to the patients)
- To explore whether routinely collected data could be used to populate the ADRe Profile

Secondary Objective

- To establish the validity and reliability of the ADRe Profile
- To explore the feasibility of linking the electronic ADRe Profile to GP electronic records
- To report how ADRe Profile contributes to efficient collaboration of the multiprofessional team (nurses, care assistants, pharmacists, GP's) in monitoring the effects of patients' medications
- To report how ADRe contributes to patient-centered care
- To estimate costs associated with ADRe implementation

Primary Endpoint

Phase 1

- Content validity index (overall assessment of validity of the instrument)
- Construct validity (overall assessment of validity of the instrument)
- Cognitive interviews: Enhanced understanding how participants answer the ADRe questions.
- Inter-rater reliability of patient versus nurse-researcher completed ADRe Profile (Cohen's Kappa) - (To determine how much of the potential variability of the records is due to errors in measurement, to estimate a degree to which service users accurately evaluate their symptoms when compared with a nurse researcher, to determine suitability of ADRe for patient self-completion. Cohen's Kappa will be calculated.) [Time Frame: 4 months from the start of the study]
- Level of completion of all items in the video call-completed ADRe Profile. (Comparison of completeness of the ADRe Profile completed through a video

call with ADRe Profiles previously completed in person, suitability of ADRe Profile for video call completion.) [Time Frame: 4 months from the start of the study]

- Calculated percentage and described nature of items on the ADRe Profile that can be populated from accessing the nursing and medical notes. (Establishing the overlap of information - the number and nature of the ADRe items that have previously been collected and recorded in the patients' nursing and medical notes.) [Time Frame: 16 months from the start of the study]

Phase 2

- Clinical impact on service users, including new problems identified (number and nature) and problems addressed (number and nature). [Time Frame: 16 months from the start of the study]
- Number of patients with a change in signs and symptoms related to adverse effects of prescribed medicines. Care quality/ clinical gain/ benefit to patients as recorded in notes and on the Profile by the number and nature of all health problems addressed, particularly serious adverse events. [Time Frame: 16 months from the start of the study]
- Prescription changes (number of patients with changes in prescription regimens: drug or dose. Number and nature of changes). [Time Frame: 16 months from the start of the study]

Phase 3

- Description of stakeholder views on ADRe Profile implementation effectiveness (survey rating of the ADRe Profile - Likert scale). A brief survey will be distributed to the main stakeholders (patients, nurses, GP's and pharmacists) following completion of Randomised Controlled Trial. [Time Frame: 22 months from the start of the study]
- Description of stakeholder views on ADRe Profile implementation feasibility (eliciting interview themes). Semi-structured interview with the main stakeholders (patients, nurses, GP's and pharmacists) to explore their views on feasibility of ADRe Profile integration in GP practices. [Time Frame: 22 months from the start of the study].

Secondary Endpoint

- Calculation of the average nurses', GP's and pharmacists' length of time per one ADRe Profile completion. Average length of the health professionals' time involvement with one ADRe Profile. [Time Frame: 16 months from the start of the study]. Phase 2
- Calculation of the cost of nurses', GP's and pharmacists' time, based on average national salary cost per hour. Estimated costs of ADRe implementation in GP practices. [Time Frame: 16 months from the start of the study] Phase 2

- Description of the main stakeholders' views on multidisciplinary collaboration (eliciting interview themes). Semi-structured interview with the main stakeholders (patients, nurses, GP's and pharmacists) to explore their views on whether and how ADRe Profile contributed to multidisciplinary collaboration between nurses, doctors and pharmacists. [Time Frame: 22 months from the start of the study] Phase 3
- Description of the patients' views on the contribution of ADRe Profile to patient-centered care (eliciting interview themes). Semi-structured interview with the patients to seek their views on whether and how ADRe Profile contributes to patient-centered care. [Time Frame: 22 months from the start of the study] Phase 3

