3.1 Number of Subjects and Subject Selection

Content Validity Index sample size n = 10

Participants: a convenience sample of 2 GPs, 2 pharmacists, 2 nurses working in general practice/community and 2 care assistants working in general practice/community and 2 patients

Recruitment strategy: advertise in research networks and the university

Contrast group sample size n = 2x20

Participants: a convenience sample of up to 20 service users > 64 who do not take prescribed medicines daily.

Recruitment strategy: Advertise in research networks and the university

Cognitive interview sample size n = 5

Participants: a convenience sample of 1 patient, 1 nurse working in general practice/community, 1 care assistant working in general practice/community, 1 GP + 1 pharmacist

Recruitment strategy: Advertise in research networks and the university

Inter-Rater Reliability sample size n = 20 + 30 = 50

Participants: 20 service users from 2 general practices, >64, with >4 prescribed medicines.

Recruitment strategy: Approach cluster areas in Swansea Bay UHB and Hywel Dda UHB. Invitation by letter and/or email. General practice to identify suitable patients and approach them to invite for participation.

Randomised Controlled Trial sample n = 60

Participants: 6 new general practices x 10 patients and practice / district nurses or nurse assistants

SU Non CTIMP Healthcare Research Protocol

Recruitment strategy: approach all 8 GP clusters in Swansea Bay UHB and 7 clusters in Hywel Dda UHB by post and/or email. General practice to identify suitable patients and approach them to invite for participation.

Calculation of the sample size:

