7.5 Statistical Analysis

We are combining quantitative and qualitative methods of analysis to capitalize on the respective strengths of each of the approaches. The mixed methods will help to evaluate the intervention effect from a patient perspective, as well illustrate the conclusions derived from the quantitative data with stakeholder insight (Bharmal et al., 2018).

The overall design is sequential: QUAN Phase 1 informs QUAN + qual Phase 2, which informs convergent design Phase 3 (QUAL + quan), Itemised methods of analysis are described below:

Content Validity Index (CVI)

To be measured using Lynn's (1986) method:

Experts will rate each item using a four-point ordinal scale (1 = not relevant, 2 = somewhat relevant, 3 = quite relevant, and 4 = highly relevant)

Number of experts rating the item 3 or 4 will be divided by total number of experts
Result of 0.78 or above will be accepted as having met the validity threshold.
Scale content validity ratio will be calculated as a proportion of total items judged against content valid items.

Cognitive interviews

SU Non CTIMP Healthcare Research Protocol

Think aloud technique combined with participant confidence rating (the degree of confidence participant has in their answer) and observation (eg. To find out where people start reading, whether they look for instructions, whether they take longer to answer any particular questions)

Contrast group construct validity

Numerical value will be added to ADRe responses (0 for 'no' answers and 1 for 'yes' or 'worse' answers. Numbers of problems will be compared for the group (n=20) without prescribed medicines and the group (n=20) that is prescribed > 4 medicines (these are participants of 1.2 ADRe testing).

Inter-rater Reliability (IRR)

Cohen's Kappa will be calculated (Cohen, 1960) to compare patient and researcher completion.

Randomised Controlled Trial

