Data will be entered into excel via the electronic version of ADRe, imported into SPSS and described for the before and after ADRe administrations. Statistical analysis: differences between before and after the intervention will be calculated for: number and nature of problems addressed, prescription regimens, and NHS use. The impact of GP practice, age, diagnoses, and medicines' use (numbers and types of medicines prescribed) will be described and accounted for in exploratory bivariate and multivariate regression analyses. To explore the recorded changes and potential for further clinical gains, putative aetiologies of service users' signs and symptoms will be ascribed, using clinical information from medical and nursing records, including, but not restricted to, information on ADRe, and the list of medications prescribed (and over the counter). The ascription will be checked by supervisors using manufacturers' literature and formularies. Juxtaposition of ADRe and medication lists will generate suggestions for changes to improve the processes and possibly the outcomes of care. The prevalence of problems on the before and after profiles will be compared with two by two contingency tables, using McNemar's test for related dichotomous variables (Altman 1991).

Survey

Data will be described using the Statistical Package for Social Sciences (SPSS) and later combined with the interview results.

Interviews and recorded ADRe consultations

All interviews (and relevant parts of ADRe consultations) will be transcribed verbatim by the researcher/professional transcriber and anonymised. Transcripts will be

SU Non CTIMP Healthcare Research Protocol

coded, categorised, analysed and interpreted alongside the data of all completed cases, to identify, analyse and report patterns within data (Braun and Clark, 2006). The transcripts will be analysed by the team using the constant comparative method which will provide a systematic, re-iterative way of comparing and contrasting emerging codes, categories and concepts and ensure that theoretical perspectives are embedded in the description of change. Two researchers ([name]) will ensure validity of the analysis and verify interpretation. Disagreements will be resolved through discussion at team meetings. Diaries/logs will also be analysed in association with interview transcripts.

Triangulation

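### Cohen's kappa is the only statistic for patient against nurse-researcher completion and cannot show whether patients miss or over-report problems; reporting the discordant counts and related measures beside it is a cheap improvement

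*Combined protocol and SAP*

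**What the plan says.** Section 2.1 lists agreement between patient-completed and nurse-researcher-completed Profiles among the Phase 1 primary endpoints. It gives three purposes: to find how much variability in the records is measurement error, "to estimate a degree to which service users accurately evaluate their symptoms when compared with a nurse researcher", and "to determine suitability of ADRe for patient self-completion". The last serves a primary objective, whether patients can complete parts of the Profile themselves.

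For the analysis, section 7.5 says only that "Cohen's Kappa will be calculated (Cohen, 1960) to compare patient and researcher completion"; the synopsis says the same. There is no confidence interval, no threshold for acceptable agreement, no statement whether kappa is per item or pooled, and no measure that separates the two kinds of disagreement. The one paired test in the plan serves another comparison: "The prevalence of problems on the before and after profiles will be compared with two by two contingency tables, using McNemar's test".

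On numbers, section 3.1 gives "Inter-Rater Reliability sample size n = 20 + 30 = 50", but its participant line describes only 20 service users, and the endpoint's time frame in section 2.1 is 4 months. Section 7.5 codes answers as "0 for 'no' answers and 1 for 'yes' or 'worse' answers", though it says so for the contrast-group analysis.

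**The concern.** How accurately patients report, judged against a named comparator, is a question with a direction. Patients may leave out problems the nurse researcher records, or record problems the nurse researcher does not. The two errors have different consequences for self-completion. A problem left off a self-completed Profile gives the pharmacist or prescriber nothing to review, whereas an extra one can be looked at and set aside. A statistic that treats the two alike cannot inform that choice.

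The primary objective also asks about parts of the Profile, so results are needed by item. At item level kappa depends on how common the problem is, so a single value without the underlying table can be misread.

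**Working it through.** The plan states no target kappa, precision or item prevalence, so there is no derived figure to reproduce. Its only number is 20 + 30 = 50, which is correct. Binary coding is assumed for kappa, as in the contrast-group analysis.

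Notation per item: *a* both report, *b* patient only, *c* nurse researcher only, *d* neither; n = a + b + c + d. Then

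- observed agreement Po = (a + d)/n
- chance agreement Pe = [(a + b)(a + c) + (c + d)(b + d)]/n²
- kappa = (Po − Pe)/(1 − Pe)
- sensitivity relative to the nurse researcher = a/(a + c); specificity = d/(b + d)
- positive agreement = 2a/(2a + b + c); negative agreement = 2d/(2d + b + c)

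**1. Direction.** Swapping *b* and *c* leaves Po and Pe unchanged, so kappa is unchanged. For n = 50:

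| | Patients over-report | Patients miss |
|---|---|---|
| (a, b, c, d) | (10, 10, 0, 30) | (10, 0, 10, 30) |
| Po | 40/50 = 0.80 | 40/50 = 0.80 |
| Pe | (20×10 + 30×40)/2500 = 0.56 | (10×20 + 40×30)/2500 = 0.56 |
| kappa | 0.24/0.44 = 0.545 | 0.24/0.44 = 0.545 |
| sensitivity | 10/10 = 100% | 10/20 = 50% |
| specificity | 30/40 = 75% | 30/30 = 100% |
| positive agreement | 20/30 = 0.67 | 20/30 = 0.67 |
| negative agreement | 60/70 = 0.86 | 60/70 = 0.86 |

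For n = 20, (4, 4, 0, 12) and (4, 0, 4, 12) also both give 0.545. Positive and negative agreement are symmetric too. Direction is visible only in the discordant counts and in sensitivity and specificity.

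**2. Prevalence, with raw agreement held at 90% (n = 50).**

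- (23, 2, 3, 22): Pe = 0.50, kappa = 0.40/0.50 = 0.80
- (3, 2, 3, 42): Pe = (5×6 + 45×44)/2500 = 0.804, kappa = 0.096/0.196 = 0.49
- (1, 2, 3, 44): Pe = 0.870, kappa = 0.23

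**3. Prevalence, with rater quality held constant.** Assumptions, not from the documents: each rater independently has sensitivity 90% and specificity 95% for the true state, and prevalence runs from 5% to 50%. At 5%, both report with probability 0.05×0.81 + 0.95×0.0025 = 0.0429, and each rater reports with probability 0.0925. Kappa medians are over simulated datasets in which kappa is defined.

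| Prevalence | Raw agreement | Median kappa, n = 20 | Median kappa, n = 50 | Patient sensitivity relative to nurse |
|---|---|---|---|---|
| 5% | 90% | 0.35 | 0.39 | 0.0429/0.0925 = 46% |
| 10% | 90% | 0.57 | 0.56 | 62% |
| 20% | 89% | 0.68 | 0.67 | 75% |
| 50% | 86% | 0.70 | 0.72 | 86% |

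At 5% prevalence, kappa is 0 or below in about 39% of defined values with 20 pairs and about 11% with 50. It is undefined in about 5% of samples with 20 pairs and almost never with 50.

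**4. The same check on the added measures.** In this model sensitivity relative to the nurse researcher also moves with prevalence (last column), because the comparator is imperfect. With 20 pairs at 5% prevalence it is undefined in about 14% of samples, more often than kappa, and exactly 0 in a further 27%. Exact 95% intervals are wide: 10/20 gives 27% to 73%, 4/8 gives 16% to 84%, and 1/2 gives 1% to 99%.

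**The case against.** Kappa is a conventional choice for inter-rater reliability, which is how the endpoint is labelled, and it fits the first stated purpose. That stands, and is why kappa should stay. It does not cover the other two purposes.

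A reader might infer that kappa collapses for uncommon problems and that self-completion would be wrongly rejected as a result. The documents do not support that. They give no item prevalences or number of items, do not say that kappa is per item, and set no threshold or rejection rule. Pooling over items would soften the prevalence effect, though not the directional one. The stated total is 50 pairs, at which the effect is much milder than at 20. The 20-pair figures matter only if the 4-month time frame restricts the analysis to Phase 1 patients, which the plan leaves unclear. A kappa of 0 is also a fair summary when the only reported case was reported by one rater and not the other.

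A reader might also infer that sensitivity and specificity should replace kappa as the basis for judging self-completion. Step 4 shows why not: they share the prevalence problem, and for rare items sensitivity fails more often than kappa. Nor is the nurse researcher's record a gold standard, since section 1.1 describes the Profile as combining observation with what patients report.

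Finally, sections 4.4 and 4.5 pair self-completion with nurse or researcher completion, so a problem missed on self-report is not thereby missed in participants' care during the study. What is at stake is the conclusion about later use.

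**Conclusion.** The point holds as a cheap improvement. As written, the plan cannot tell missed problems from over-reported ones in a primary endpoint that is partly about accuracy. This is exact algebra: it needs no assumption about prevalence, holds at 20 or 50 pairs, and holds for per-item or pooled kappa.

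The prevalence effect is real but its size is conditional. Under the assumed rater quality, median kappa falls from 0.70–0.72 at 50% prevalence to 0.35–0.39 at 5%, with raw agreement of 86% to 90%; at 10% and 20% the fall is milder. Whether any Profile items are that uncommon cannot be settled from the documents. This supports showing prevalence and the full table beside kappa, not dropping kappa.

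**What to change.** In sections 2.1 and 7.5 (and the matching synopsis text):

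- Keep Cohen's kappa and add a confidence interval. State whether it is per item, pooled or both, and whether the 20 Phase 1 pairs or all 50 are used.
- Beside it, report per item the 2x2 table with patient-only and nurse-only counts, positive and negative agreement, and sensitivity and specificity relative to the nurse researcher with exact 95% intervals. Say that these are relative to an imperfect comparator.
- Interpret suitability for self-completion on these together, not on any one of them.
- For any figure pooled over items, bootstrap by patient, because items within a patient are not independent.
- Report items with too few cases as uninformative, neither passing nor failing.

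The cost is wording and some extra tables. Section 4.5 and the case report form list in section 8.3 (Forms 09 and 10) already provide for both Profiles, so no new data are needed. The downside is that intervals will be wide and, for rare items, sensitivity will be unstable or undefined.
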